3.2 Intervention phase procedures

3.2.1 Randomization

For this trial, the unit of randomization will be the individual participant. Participants will enroll and complete a baseline survey before being randomized to a study arm, a qualitative interview and/or audio-recording of their visit by research staff with the use of a REDCap randomization instrument, based on an allocation table. Results of randomization will be documented in REDCap.

Individuals will not be considered participants until they are randomized. Prior to being randomized, if an eligible patient participant does not wish to continue with study procedures, they will be considered as a “decline to participate.” If they do not wish to continue with study procedures after the point of randomization, they will be considered “dis-enrolled” (see dis-enrollment procedures).

Intervention arm randomization

Randomization (#1) to the study’s intervention (HIV prevention DST) or control arms will occur immediately before receipt of the intervention.

In-depth interview and audio-recording randomization

After enrollment in the study and randomization to the DST or control arms, participants will then be randomized to determine if they will be invited to conduct a qualitative interview or audio-recording of their counseling visit. This randomization will be based on participant’s response during the eligibility screening regarding racial/ethnic identity.

For participants who self-identify as Black or Latina, or multiracial including Black or Latina, a random number generator will be used within each study arm (those randomized to the DST or control) to determine if the participant will be invited to complete an in-depth qualitative interview after their visit or have their counseling session audio-recorded. If yes, the participant will be offered the opportunity to complete an interview or audio recording and consented if they agree.

Participants who do not identify as Black or Latina, or multiracial, will only be randomized to have their counseling session audio-recorded or not. If yes, participants will be invited to participate and consented if they agree.

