3.2.2 Blinding

Given the nature of the intervention, blinding of participants to which intervention they receive (DST or not) will not be feasible. Clinicians and counselors in the clinic will not be alerted to whether participants used the DST or not; however, participants may discuss information in the DST, unmasking the study arm. Consequently, clinicians and counselors will unlikely be blinded to study interventions. However, at follow-up, study personnel conducting surveys by phone will not be aware of participants’ study arm; assignment will be concealed in a different page of the participant’s record. Consent forms intentionally do not disclose the specific outcome of interest (i.e. PrEP initiation), so as not to influence participant behavior. Additionally, participants will not be aware of their arm assignment until after they have been consented. Study staff will be blinded during quantitative data analysis of participants use of the DST or not. Qualitative data will not be blinded as study participants will be asked about use of the DST.

3.2.3 Baseline procedures (see below changes we will be making to the study procedures based on COVID-19)

Patients

The baseline procedures for patient participants are as follows:

On the day of enrollment:

- Individuals will be handed a laminated information card about the study and eligibility criteria when they present to the front desk for check in. Eligibility criteria on this sheet will include:
 - Identify as a woman
 - Age 18 years old or over
 - Not known to be living with HIV
 - Not known to be taking PrEP
 - English speaking
 - Interested in participating in the study
- If patients self-identify as eligible and interested in learning more about the study, they will be instructed to hold onto the laminated card (indicating to the research assistant that they would like to be approached). If they are not interested in participating, patients will hand this card back to front desk staff.
- Research staff will approach patients who have held onto the card in the clinic waiting room before their appointment and invite them to be screened for study eligibility in a semi-private space. Research staff will share a brief description of the study and assess eligibility using a verbal eligibility checklist.

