 - Researchers will also ask patients if they self-identify as Black or Latina, or multiracial including Black or Latina, to determine eligibility for randomization to interviews or audio-recordings after randomization to the study.
- If participants are eligible, they will be consented to enroll in the study.
 - If individuals decline to enroll or are ineligible, the reason for ineligibility will be recorded or reason for declining if shared.
- All participants will be asked to complete a contact information form in REDCap on a tablet computer and complete a pre-visit survey collecting information on experience with and knowledge of HIV prevention.
- Participants will then be randomized to the intervention arm (DST) or control (standard care).
- Based on response during eligibility screening regarding racial identity, participants will then be randomized to determine if they will be invited to conduct a qualitative interview or audio-recording of their counseling visit. Specifically:
 - Participants who identify as Black or Latina will be randomized to participate in a qualitative interview or audio-recording
 - Participants who do not identify as Black or Latina will be randomized only to audio-recording or not.
- Participants who are randomized to participate in an interview will be invited to have an interview the same day if the qualitative interviewer is available. Interviews will

be conducted either in-person in a private space, or over Microsoft Teams or Zoom (using a hotspot), both HIPAA compliant video conferencing programs. Interviews will be conducted within 1 week of the clinic visit.

- Participation in each study activity (participation to be randomized to the DST or standard care, participation in a qualitative interview, and/or participation in an audio-recorded clinic visit) will require a unique consent. Participants randomized to the audio recordings will be consented for the audio recording at this time. Participants who are randomized to participate in an in-depth interview and interested in being interviewed, will be consented by [name], a member of the study team, or another study staff member, on the day of the interview before the interview begins.
 - If participants decline to enroll in additional study components, their reason for declining will be recorded and they will be allowed to continue with primary study activities.

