- Research staff will give the tablet-based DST to participants randomized to the intervention arm to complete prior to their visit.
- All participants will then have a clinical visit with their healthcare provider, per standard clinic protocol.
 - During the visit, participants who are randomized and consented to audio-recordings will have their visits audio-recorded on a HIPAA-compliant recorder.
- After the clinical visit, each study participant will complete a post-visit survey about their demographics, HIV prevention method choice and experience of the counseling they received. If a participant must leave the clinic without completing her post-visit survey due to time constraints (and not because she wants to withdraw from the study), study staff will attempt to contact the participant using the contact information provided and request that they complete the post-visit survey by phone or email.
 - If the patient does not complete the post-visit survey within 72 hours of their initial visit, study personnel will continue to attempt to have them complete the post 72-hours version of the post-survey (in which the time-sensitive questions pertaining to satisfaction with choice and quality of interpersonal care have been omitted) up to one month after the initial visit.
- Participants will receive a \$20 gift certificate after completion of post-visit survey on the day of enrollment. If a participant does not complete the post-survey on the day of their appointment a \$20 gift certificate will be sent by mail after completing the survey by the RA.
- After completing the post-visit survey, participants who completed an audio-recorded session will receive an additional \$20 gift certificate.
- After the post-visit survey, participants who consented to participate in an in-depth interview will complete the interview in a private room in the clinic immediately following their appointment (in person or via video conference), or schedule the interview with research staff to take place within one week of the visit. After completion of the interview, participants will be compensated with a \$40 gift certificate. Details regarding interview procedures can be found in Section 7.4.
- Study staff will provide each patient with a flyer summarizing the timing of follow-up at three months and providing contact information for study staff in case a participant changes their contact information or wishes to dis-enroll.

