- Participants will be offered the opportunity to take or receive FDOH informational materials about HIV prevention or have them sent over email, text, or mailed at the end of the study. Patients who decide not to participate in the study but want information about HIV prevention, will be offered the same materials by the research staff. Research staff will have these informational materials with them in clinic.

In the context of COVID-19, study procedures will be adjusted in an ongoing fashion to meet the evolving requirements and protocols of the Duval County Health Department based on consistent communication with Duval DOH leadership. At this time, we will be making the following changes, developed in partnership with DOH clinical staff, to meet DOH requirements, adjust to changes in clinic flow, and enhance safety for patients, clinic staff, and study staff:

Screening

- Patients who go into the clinic to check in for their appointment will be handed a piece of paper with the information about the study and eligibility criteria (instead of a reusable laminated card as originally described).
 - If patient does not go into the clinic to check in, a clinic staff will mention the opportunity to participate in the study over the phone during phone check in and let the patient know where they can find the study staff to learn more. Study staff will have the informational flyers available at their table for patients that check into their appointments over the phone.
- If study staff is stationed outside, patients interested in participating in the study will be instructed to go into the breezeway outside to meet with the research staff from a distance.
- If study staff is inside, patient interested in participating in the study will be instructed to hold onto their paper and a study staff will approach them while keeping their distance. Patients inside the clinic who are uninterested in the study, will be instructed to throw out the flyer.

Eligibility

- When patients exit the building, they may approach research staff from a distance (staying at least 6 feet away) at the study table. Research staff will share a brief description of the study and assess eligibility using a verbal eligibility checklist. Research staff will be wearing masks at any time they are talking to or within 6 feet of patients.

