- In the introduction to the study, research staff will explicitly state upfront that if the patient feels uncomfortable at any point talking about the study, they can simply say “stop” and the research staff member will stop study activities. We know this is particularly important in cases where there may potentially be children present (and have planned consent and data collection activities accordingly as well).

Consenting

- If eligible, participant will be consented.
 - To reduce exposure, we will audio record the consent script for participants to listen to through disposable headphones. They will be handed an iPad to read along with the consent. Participants will still be able to ask research staff questions about the study after listening to the consent script.
 - If consenting will take place from the study table outside of the clinic or from within participant's car:
 - *At study table*: Sitting 6 feet apart, at the study table outside of the clinic patient will listen to an audio-recording of the form and/or read along on the iPad. The study table will be out of the way of people walking by to allow for more privacy.
 - *In car*: If for some reason the patient is unable sit at the table (like weather, has children, etc.), patient will listen to an audio-recording of the form and/or read along on the iPad.
 - The study iPad will be wiped down between each step and interaction.

Baseline activities

- Participant will join research staff at study table outside, if they have not already or in a semi-private space indoors

Clinical visit

- All participants will then have a visit with their healthcare provider, per standard clinic protocol. Participants who are randomized and consented will have visits audio-recorded.
 - In the context of COVID, birth control counseling is occasionally occurring by phone while a patient remains in their car. In this case, research staff will ask providers to place their phones on speaker mode and record the counseling session from the provider's office. Providers will be counseling from private offices and will be instructed to speak at their normal volume and to keep the phone on a volume at a level that maintains patient privacy.
 - We have increased the number of audio recordings from 40 to up to 60 to account for any issues in audio quality given this change.

Post-visit activities

- After the clinical visit, each study participant will complete a post-visit survey

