Three months after the last participant has been enrolled, a study RA will submit study participants' medical record numbers to FDOH IT, to extract the following information:

- Zip code at the time of the study visit
- Insurance status at the time of the study visit
- PrEP prescription (ever) and date of prescription
- PEP prescription (ever) and date of prescription
- Dates of HIV testing and results
- Hepatitis B and C diagnoses (ever)
- Dates of STI testing and results including chlamydia, gonorrhea, syphilis and trichomonas (within 6 months and ever)

The Duval County DoH Information Technology (IT) Department will be supplied with a list of study ID numbers and medical record numbers. IT will extract relevant outcome variables and create a dataset ONLY with study ID and outcome variables; no PHI will be included in the main dataset. Only this de-identified dataset will be shared among the study team for analysis. These data will be securely transferred to UCSF for analysis, using MoveIt, an encrypted and secure file transfer program that is used by the Florida Department of Health.

The DoH IT department will also extract aggregate data by clinic during the study period of clinic patient demographics (age, race, insurance status), STI diagnoses, HIV diagnoses, and PrEP & PEP prescriptions. In addition, DoH will provide the number of clinic visits per week for the duration of the study, as well as the number of providers at each site and scope of services of each clinic.

This de-identified information will then be stored on secure servers to ensure the privacy of research participants. Information about the above processes is included in the participant's consent form for the main study.

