5. PARTICIPANT RECRUITMENT

Patient

Recruitment of study participants will be conducted by FDOH study coordinator and research assistants based on coordination with clinic directors and staff at each study site. Procedures will be tailored to meet the needs of clinic flow at each site.

Each clinic will identify a point person, likely at the front desk, who will hand a laminated information card about the study and eligibility criteria to patients when they present to the front desk for check in. If patients self-identify as eligible and are interested in participating, they will hold onto the laminated card (indicating to the research assistant that they would like to be approached). If they are not interested in participating, patients hand this sheet back to front desk staff.

Study staff will approach potential participants in the waiting room and invite them to a semi-private room where they will share a brief description of the study and assess eligibility using a verbal eligibility checklist. All recruitment, consent, and baseline activities may occur before, during or after appointments in accordance with clinic flow.

If the patient is eligible and wishes to participate, the research assistant will complete the consent process and enroll her in the study.

Providers

At the invitation of the clinics, research staff will attend provider and staff meetings. The intervention will be discussed, study procedures will be explained, and questions will be answered. Providers and counselors will also be invited to meet individually with study staff to answer questions about the study, and audio recording of clinic visits of participants who consent.

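### Protocol section 5 lets recruitment, consent and baseline activities take place during or after the appointment, which read literally permits randomisation after counselling, contrary to the pre-visit order elsewhere

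*Protocol*

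**What the plan says.** Protocol section 5 (Participant Recruitment) describes cards handed out at check-in and an approach in the waiting room, then adds a general allowance: "All recruitment, consent, and baseline activities may occur before, during or after appointments in accordance with clinic flow".

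The detailed text fixes an order:

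- Protocol 3.2.1: "Participants will enroll and complete a baseline survey before being randomized to a study arm". The same section places arm randomisation directly before the intervention is received.
- Protocol 3.2.3 (Baseline procedures): staff approach patients "in the clinic waiting room before their appointment and invite them to be screened for study eligibility". Once consented, participants "complete a pre-visit survey collecting information on experience with and knowledge of HIV prevention" and are then randomised. Next, "Research staff will give the tablet-based DST to participants randomized to the intervention arm to complete prior to their visit". The provider visit follows.
- Protocol 3.2.3, COVID-19 changes: under Eligibility, "When patients exit the building, they may approach research staff from a distance". After the consent and baseline steps, under Clinical visit, "All participants will then have a visit with their healthcare provider".
- SAP 1.2 and 1.6: approach comes before the appointment, and the DST is used immediately before the provider visit.

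The eligibility lists (Protocol 4.1, SAP 1.3) contain nothing about whether counselling at the index visit has started. The primary outcome window is three months from the visit (Protocol 7.1, SAP 3.3.1). The chart extract supplies "PrEP prescription (ever) and date of prescription" (Protocol 3.2.5).

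**The concern.** If enrolment may follow the appointment, so may randomisation, and a trial of a pre-visit tool then includes women for whom the visit is already over. Four things follow for such a woman.

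- **Effect.** The DST is meant to prompt questions to the provider (Protocol 1.1). Used after counselling, it cannot affect that visit, yet she counts fully in the primary intention-to-treat analysis. The per-protocol rule in SAP 2 would not pick her up either: it asks only whether the DST was received and used for at least a minute, not when.
- **Outcome.** The window opens at the visit, not at randomisation, so a prescription written before she was randomised could count.
- **Baseline.** Her pre-visit answers would be given after counselling. They would still meet SAP 4.1, which defines baseline only relative to the intervention.
- **Traceability.** Protocol 9.1.2 says REDCap tracks user actions by time, but no record of when counselling began is described, and the chart gives a date rather than a time. The order of events within one day may not be recoverable.

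**Working it through.** **1. Does the text permit it?**

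| Step | Protocol 5 | Protocol 3.2.1 and 3.2.3; SAP 1.2 and 1.6 |
|---|---|---|
| Approach | before, during or after appointment | before appointment |
| Consent to main study | before, during or after | before visit |
| Baseline (pre-visit) survey | before, during or after | before visit |
| Arm randomisation | not named; must follow the two rows above | after survey, before DST |
| DST | not named | before visit |

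Consent and survey precede randomisation. If they may follow the appointment, randomisation may too, and no eligibility criterion stops it.

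Part of the sentence has a proper reading. Protocol 6.1 calls the post-visit survey a baseline survey, and interview consent can follow the visit (Protocol 3.2.3 and 5.1.1). Neither explains why all recruitment, or consent to enrol, could come afterwards.

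The COVID-19 sequence is fairly clear that the visit follows enrolment. Leaving the building there most naturally means leaving after check-in.

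**2. Reproducing the planned sample size.** Inputs (Protocol 7.2, SAP 1.5): 5% v 15%, two-sided alpha 0.05, power 80%.

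n = [1.96√(2p̄(1−p̄)) + 0.84√(p₁(1−p₁) + p₂(1−p₂))]² / δ², with p̄ = 0.10 and δ = 0.10, gives 140.1 per arm.

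Continuity-corrected: n/4 × [1 + √(1 + 4/(nδ))]² = 159.5, so 160 per arm and **320 in total**, as stated. Without the correction it is 141 per arm, 282 in total.

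**3. Illustrating dilution.** Let f be the share randomised after counselling; the documents do not give it. With no DST effect in these women, the intervention rate is 5% + 10% × (1 − f). If they keep half the effect, it is 5% + 10% × (1 − f/2). Allocation is 192 per arm (SAP 1.2), all analysed.

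Power = Φ{[(δ − c)√n − 1.96√(2p̄(1−p̄))] / √(p₁(1−p₁) + p₂(1−p₂))}, with c = 1/n (corrected) or 0 (uncorrected).

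Example, f = 10%, corrected: δ = 0.09 and p̄ = 0.095. The numerator is (0.09 − 0.0052) × 13.86 − 1.96 × 0.4147 = 0.362. The denominator is 0.410. Φ(0.884) = 0.812.

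The exact column enumerates the uncorrected chi-square test.

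| Scenario | Difference (points) | Corrected | Uncorrected | Exact chi-square |
|---|---|---|---|---|
| f = 0 | 10 | 0.875 | 0.907 | 0.921 |
| f = 5%, no effect | 9.5 | 0.846 | 0.884 | 0.898 |
| f = 10%, no effect | 9 | 0.812 | 0.855 | 0.871 |
| f = 20%, no effect | 8 | 0.728 | 0.784 | 0.800 |
| f = 10%, half effect | 9.5 | 0.846 | 0.884 | 0.898 |
| f = 20%, half effect | 9 | 0.812 | 0.855 | 0.871 |

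In the no-effect case, power reaches 80% at f = 0.115, 0.180 and 0.200 on the three methods.

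**4. Restricting to women randomised before counselling.** Timing relative to the visit is settled before randomisation, so this comparison stays valid if timing is known. At full effect, n per arm is 192 × (1 − f) rounded down:

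| f | n per arm | Corrected | Uncorrected | Exact chi-square |
|---|---|---|---|---|
| 10% | 172 | 0.833 | 0.874 | 0.893 |
| 20% | 153 | 0.781 | 0.834 | 0.851 |

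**The case against.** The best defence is that this is a wording slip which the specific text already overrides. Section 5 itself describes arrival steps, the disputed sentence names neither randomisation nor the DST, and staff who randomised after the visit would breach Protocol 3.2.3 and SAP 1.2 whatever section 5 allows. An appointment may also include waiting time, so enrolment during it can still precede counselling; only enrolment after it necessarily conflicts. The late share is assumed, and by exact chi-square power does not fall below 80% at any f shown. The no-effect case is pessimistic, since a DST used after the visit could still prompt a prescription within three months. REDCap times might expose a late enrolment when the pre-visit survey, randomisation and post-visit survey fall close together. Finally, a shorter edit to the sentence would remove the contradiction.

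Much of this stands. Staff who enrol everyone before the visit satisfy both texts, the frequency is unknown, and events before randomisation are balanced between arms in expectation. But section 5 gives an unqualified permission covering recruitment and consent, and it also tells sites to tailor procedures to clinic flow. Staff relying on it could reasonably not log a late enrolment as a deviation. REDCap times are imperfect evidence because post-visit surveys can be delayed. The point about waiting time is met by drawing the line at the start of counselling.

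**Conclusion.** The contradiction is real and should be fixed. Read literally, Protocol section 5 permits randomisation after counselling, against the pre-visit order in the detailed procedures and the SAP, and nothing in the eligibility criteria prevents it. The consequence is dilution of the primary contrast, possible counting of prescriptions that precede randomisation, and baseline answers taken after counselling. It does not favour either arm.

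The size depends wholly on the unknown f. On the formula behind the planned 320, a late share of up to about 12% leaves power at 80% or more even with no effect in late women; on exact chi-square the limit is about 20%. These figures assume the plan's 5% and 15% rates and all 384 women analysed. They show what the permission could cost, not a demonstrated loss of power. Confidence is high that the texts conflict; whether anyone was randomised late cannot be judged from the documents.

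**What to change.** Replace the section 5 sentence with:

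> *Main-study screening, consent, the pre-visit survey, randomisation to study arm and, in the DST arm, use of the tool are completed before provider counselling begins; a woman whose counselling has already started is not randomised at that visit. The audio-recording/interview randomisation, its consents and all later study steps follow the order in sections 3.2.1 to 3.2.5.*

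Then:

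- Add an exclusion to Protocol 4.1 and SAP 1.3: *Provider counselling at this visit has already begun.*
- In the COVID-19 Eligibility text, state that women who approach staff on leaving the building do so after check-in and before counselling.
- Record in REDCap, at randomisation, whether counselling had begun.
- If any women were already randomised late, keep intention-to-treat as primary, report their number by arm, and add a sensitivity analysis restricted to women randomised before counselling.

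The cost is one sentence, one criterion in two lists, one clause, one REDCap field and a staff instruction. The real downside is that women identified late cannot be enrolled that day: 0.10 × 384 ≈ 38 at f = 10% and 0.20 × 384 ≈ 77 at f = 20%. Recruitment could take longer if late enrolment is common.
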